12 SCREENING AND ON-STUDY TESTS AND PROCEDURES

Table 2. Schedule of Study Tests and Procedures

Description	Within 6 months	Screening: Within 14 days prior to catheter placement	Screening: Within 5 days prior to PVSRIPO	Catheter Placement biopsy, PVSRIPO infusion	After Completion of Infusion	Post infusion (follow-up period) ^a						
Week						0	1	2	4	8	16, 24, 32, 40, 48	
Day		Within 14 days prior to catheter placement	Within 5 days prior to PVSRIPO	0	0	1	7	14	28	56	112, 168, 224, 280, 336	
General Evaluations												
Physical Exam		X	X			X ^b	X	X	X	X		X
Neurologic Exam		X	X			X ^b	X	X	X	X		X
Performance Status		X	X				X	X	X	X		X
Adverse Events ^h	X	X	X			Continuous						
Laboratory Evaluations												
Poliovirus Immunization Booster	X											
CBC w/diff		X				X		X	X	X		X
CMP		X				X		X	X	X		X
PT, aPTT		X										
Serum Pregnancy Test		X	X ^c									
Serum for LSQ and anti-tetanus toxoid IgG	X											
Whole blood for immunologic analysis and/or poliovirus titer (up to 10 mL, except for 4 mL on Day 1 and 6 mL on Day 14)	X	X				X	X	X	X	X	X (at 16 and 24 wks) ^d	
Whole blood for immunologic analysis (not to exceed 3 mL/kg in a 24 hr period or 7 mL/kg in a 8 week period)	X ^e	X ^e					X ^e	X ^e	X ^e	X ^f	X (at 16 and 24 wks) ^{d, f}	
Disease Evaluations												
MRI			X		X ^g (based upon date of enrollment)				X	X		X
CT Scan				X								
Biopsy				X								
Treatment												
PVSRIPO				X								

^a Starting with Day 7 (Week 1), all tests and procedures have a 7-day plus or minus window.

^b Daily after infusion until discharged from hospital

^c Serum pregnancy test, if appropriate, within 48 hours of catheter placement and PVSRIPO

^d At the discretion of the Principal Investigator, an additional blood sample at least 2 years post study drug infusion may be obtained.

^e Whole blood draws for immunologic analysis may be taken (up to 36 mL) at the discretion of the Investigator, but should remain consistent with allowable volumes for pediatric patients depending upon the weight of the child (per Duke policy, the maximum blood volume drawn for research should not exceed 3 mL/kg in a 24 hr period or 7 mL/kg in an 8 week period).

^f At 8, 16, and 24 weeks, up to 76.5 mL of whole blood may be drawn for immunologic analysis (please refer to Duke blood volume policy mentioned above).

^g Prior to October 31, 2019, MRI to track Magnevist® containing infusate should have been obtained within 4 hours after completion of infusion. This MRI after the infusion was without gadolinium enhancement, but this MRI will not be performed on patients enrolled after October 31, 2019. All other MRIs in the study include gadolinium enhancement.

^h Adverse events directly related to required screening procedures should be recorded.

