9.1.5 Definition of Unacceptable Toxicity

Toxicities will be graded according to the NCI CTCAE version 4 criteria. Any Grade 3 or any Grade 4 toxicity that is not reversible within 2 weeks, any life-threatening event deemed related to the study drug, or any treatment-related death will be considered unacceptable.

Any Grade 2 or higher autoimmune toxicities, particularly those affecting vital organs (e.g. cardiac, renal, CNS), will be considered an unacceptable toxicity, if it occurs within 2 weeks post-infusion. Grade 3 or higher surgical complications from insertion of the catheter are considered an unacceptable toxicity.

Exceptions to these unacceptable toxicities are as follows:

- Events associated with the biopsy procedure/catheter placement: Seizures or hemorrhages occurring during anesthesia or the biopsy/catheter insertion proper prior to administration of the agent if Grade 2 or lower.
- Seizures: Due to the nature of the disease under investigation in this protocol, patients may have pre-existing seizures or be susceptible to new seizures as a result of the underlying disease process. Although seizures may be defined as Grade 3 or 4 toxicities under NCI CTC, and will be reported as such in this protocol, seizures will not be considered an unacceptable toxicity if, in the opinion of the site Principal Investigator they have not increased in frequency or can be attributed to another recognized cause of increasing seizure frequency such as sub-therapeutic anti-convulsant levels or biopsy proven tumor progression.
- New or worsening neurologic deficits: Due to the nature of the disease under investigation in this protocol, patients may have an increase in pre-existing neurologic deficits or may develop new neurologic deficits as a result of tumor invasion. A new neurologic deficit, which resolves within 2 weeks after initiation of medical therapy, will not be considered an unacceptable toxicity. New neurological symptoms will not be an unacceptable toxicity if they can be ascribed to tumor progression (e.g. documented with histopathologic analyses of biopsy tissue), or they respond to treatment (e.g. oral steroids) within 2 weeks.

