12.7.5 Correlative Assessments

- Anti-tetanus toxoid IgG titer within 6 months prior to treatment
- Up to 10 mL of whole blood for tests of immunologic assays and anti-PV antibody titer at day 1 and weeks 1, 4, 8, 16, and 24 after treatment. Up to 6 mL collection of whole blood at week 2 (day 14).
- Up to 36 mL of whole blood for tests of anti-tumor immune responses within 6 months before receiving PVSRIPO, and at weeks 1, 2, and 4 and up to 76.5 mL at weeks 8, 16, and 24 after treatment. At the discretion of the Principal Investigator, an additional blood sample at least 2 years post study drug infusion may be obtained (see [Table 2](#)). Because of the large volume of the whole blood draws taken for immune monitoring, it will be essential to carefully consider the weight of each patient when determining whether a blood draw may occur, or how much blood may be drawn at a given time point. In this pediatric population the maximum blood volumes are 3 mL/kg in a 24 hour period or 7 mL/kg in an 8 week period. [Table 3](#) contains predicted blood draw volumes that are required for planned study assessments.

Table 3. Schedule of Blood Draw Volumes

Maximum blood draw volumes (mL) ^a							
	Screening		Treatment				
Day	Within 6 months (≈d -28)	Within 14 days prior to catheter (≈d -14)	1	7	14	28	56
CBC & CMP		6	6		6	6	6
PT, aPTT		1.8					
Pregnancy		2					
LSQ, tetanus titer	6						
Polio titer & immunologic analysis	Up to 10 (red top tube)	Up to 10 (red top tube)		Up to 10 (red top tube)	Up to 6 (red top tube)	Up to 10 (red top tube)	Up to 10 (red top tube)
Whole blood immunologic analysis	Up to 36 ^b (yellow top ACD tube)	Up to 36 ^b (yellow top ACD tube)		Up to 36 ^b (yellow top ACD tube)	Up to 36 ^b (yellow top ACD tube)	Up to 36 ^b (yellow top ACD tube)	Up to 76.5 ^b (yellow top ACD tube)
Daily Total	52	55.8	6	46	48	52	92.5
Total 8 week volume (day -28 through +28): 259.8 mL							

^a Volumes for standard lab tests are based on DUHS Clinical Labs volumes for patients age 8-15. For patients in the lower age range of this study and/or with a low body weight, lower pediatric volumes (for patients age 0-8) may be used. Some volumes may be higher for patients >15 years old.

^b Volumes of whole blood for immunologic analysis will be reduced as necessary to not exceed 3 mL/kg in a 24 hr period or 7 mL/kg in an 8 week period.

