13 SAFETY MONITORING AND REPORTING

The Principal Investigator is responsible for the identification and documentation of adverse events and serious adverse events, as defined below. At each study visit, the Principal Investigator or designee must assess, through non-suggestive inquiries of the subject or evaluation of study assessments, whether an adverse event (AE) or serious adverse event (SAE) has occurred.

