13.1 Adverse Events

An AE is any untoward medical occurrence in a subject receiving study drug and which does not necessarily have a causal relationship with this treatment. For this protocol, the definition of AE also includes worsening of any pre-existing medical condition. An AE can therefore be any unfavorable and unintended or worsening sign (including an abnormal laboratory finding), symptom, or disease temporally associated with the use of PVSRIPO, whether or not related to use of the PVSRIPO.

Abnormal laboratory findings with or without clinical significance are collected according to CTCAE v.4.

From the time the subject has their first study-related procedure until their last study-related procedure, all AEs must be recorded in the subject medical record and adverse events case report form. Thus, AE directly related to study-specific and required screening procedures should be reported.

AEs will be assessed according to the CTCAE version 4. If CTCAE grading does not exist for an AE, the severity of the AE will be graded as mild (1), moderate (2), severe (3), life-threatening (4), or fatal (5).

Attribution of AEs will be indicated as follows:

- Definite: The AE is clearly related to the study drug
- Probably: The AE is likely related to the study drug
- Possible: The AE may be related to the study drug
- Unlikely: The AE is doubtfully related to the study drug
- Unrelated: The AE is clearly NOT related to the study drug

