15.4.2 Primary Objective Analyses

Percentage of patients that experience unacceptable toxicity during the 14-day period post-PVSRIPO treatment will be calculated.

The proportion of patients who require low-dose bevacizumab or steroid treatment due to an inflammatory reaction secondary to an immune response to PVSRIPO treatment will be calculated. In addition, the time to initiation of such treatment will be calculated and summarized using Kaplan-Meier methodology.

Adverse events experienced by protocol subjects from the time of catheter placement will be summarized in several forms to satisfy scientific and monitoring needs, as well as various regulatory reporting needs (e.g. FDA, DCI SOC, and ClinicalTrials.gov). These include a summary of the frequency of adverse events that are possibly, probably, or definitely related to protocol treatment tabulated by the maximum grade for each type of adverse event, as well as a summary of the frequency of adverse events regardless of attribution tabulated by the maximum grade for each type of adverse event.

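### The ±7-day window on visits only 7 days apart can leave part of the 14-day toxicity period without a scheduled examination or laboratory test after discharge

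*Combined protocol and SAP*

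**What the plan says.** **Visit timing.** Table 2 puts Week 1 on Day 7, Week 2 on Day 14 and Week 4 on Day 28. Footnote a reads: "Starting with Day 7 (Week 1), all tests and procedures have a 7-day plus or minus window". Section 12.4 attaches the same one-week tolerance to each of these visits, so the footnote is not a slip.

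**What is done when.** Day 1 has an examination, CBC and CMP with no window. Under footnote b, examinations are then "Daily after infusion until discharged from hospital". Week 1 has a history, examination and immune blood but no CBC or CMP. Weeks 2 and 4 have all of these.

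**What depends on the timing.** Section 15.4.2: "Percentage of patients that experience unacceptable toxicity during the 14-day period post-PVSRIPO treatment will be calculated". The Table 4 suspension thresholds in Section 15.4.1 use the same 14-day count.

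**How events are found.** Section 13.1: "From the time the subject has their first study-related procedure until their last study-related procedure, all AEs must be recorded". Abnormal laboratory values are collected whether or not they are clinically significant. Section 13 names the means of detection: "At each study visit, the Principal Investigator or designee must assess, through non-suggestive inquiries of the subject or evaluation of study assessments".

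**What counts.** Section 9.1.5 includes "Any Grade 3 or any Grade 4 toxicity that is not reversible within 2 weeks". It also includes autoimmune toxicity of Grade 2 or higher arising within two weeks of infusion.

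**The concern.** A tolerance as wide as the interval between two visits means that the schedule no longer fixes either one. Here the two visits carry the early safety follow-up, and the second nominally closes the primary endpoint period. No text sets a minimum spacing, an assessment tied to Day 14, or a rule for placing an abnormality first seen after Day 14.

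At stake are the 14-day percentage and the suspension count. Among the first six patients, two events suspend accrual, so one missed or misplaced event can change the decision. The immune and titer samples share the windows. That matters less, because the objective is exploratory.

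**Working it through.** **1. The plan's own figures.** Table 5 was recomputed by exact binomial recursion. The rule was applied after every patient: suspend at ≥2 events for n ≤ 6, ≥3 for n = 7-9, ≥4 for n = 10-12, maximum 12.

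| True 14-day rate | Table 5: P(suspend), expected N | Recomputed |
|---|---|---|
| 0.05 | 0.030, 11.8 | 0.035, 11.75 |
| 0.10 | 0.124, 11.1 | 0.128, 11.11 |
| 0.15 | 0.262, 10.2 | 0.259, 10.21 |
| 0.20 | 0.411, 9.2 | 0.408, 9.19 |
| 0.25 | 0.560, 8.1 | 0.555, 8.15 |
| 0.30 | 0.681, 7.2 | 0.686, 7.15 |
| 0.35 | 0.792, 6.2 | 0.793, 6.24 |
| 0.40 | 0.873, 5.4 | 0.872, 5.45 |

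Table 5 reproduces to within 0.005. It takes the true event rate as the counted rate, so it presumes complete and correctly dated ascertainment through Day 14.

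**2. Permitted days.** Nominal day ± 7 (Table 2, footnote a; Section 12.4):
- Week 1: 7 ± 7 = Days 0-14
- Week 2: 14 ± 7 = Days 7-21
- Week 4: 28 ± 7 = Days 21-35

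Weeks 1 and 2 share Days 7-14, which is 14 − 7 + 1 = 8 calendar days. The interval from Week 1 to Week 2 can run from 7 − 14 = −7 days to 21 − 0 = +21 days, against a nominal 7. Week 2 has 15 permitted days, of which 7 (Days 15-21) fall after the endpoint period closes.

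**3. Two compliant schedules.**
- *Schedule A: Week 2 on Day 15 or later.* CBC and CMP are scheduled on Day 1, at Week 2 and at Week 4, and Week 4 cannot precede Day 21. No CBC or CMP is then scheduled on Days 2-14 (13 days). If Week 2 is on Day 21 and an abnormality appears after a normal Day 1 result, its onset could be on any of Days 2-21. That is 20 days, 13 inside the period and 7 outside.
- *Schedule B: Week 1 by Day 7, Week 2 on Day 7, Week 4 on Day 35.* For a patient discharged by Day 7 (an assumption, since no discharge day is given), no examination or laboratory test is scheduled on Days 8-14. The gap is 35 − 7 = 28 days. This is the longest permitted gap between CBC/CMP draws starting inside the period; from Day 1 to a Day 21 draw is 20 days.

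**4. What a counting error would do (illustration only).** The documents give no missed share, so it is assumed here. With recorded rate = true rate × (1 − missed share), the probability of suspension is:

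| True rate | 0% missed | 10% | 20% | 30% | 50% |
|---|---|---|---|---|---|
| 0.30 | 0.686 | 0.610 | 0.527 | 0.438 | 0.259 |
| 0.40 | 0.872 | 0.811 | 0.732 | 0.636 | 0.408 |

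The error can also run the other way. If late-onset abnormalities were counted in and lifted a true 0.20 to a recorded 0.25, the probability of suspension would rise from 0.408 to 0.555.

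**The case against.** A reader might infer that the whole 14-day period can pass unexamined. The documents do not support that. Day 1 is fixed, inpatient examinations are daily, and Week 1 can never fall after Day 14. Recording of adverse events is continuous and each visit includes a history, so a symptomatic event on Day 10 can still be recorded, with its onset date, at a Day 21 visit.

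A reader might also infer that the reported rate must be too low. That is not shown either. An abnormality first seen on Day 21 could be counted in or left out.

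The endpoint definition narrows the exposure further. If the two-week reversibility clause in Section 9.1.5 covers both Grade 3 and Grade 4, a brief laboratory abnormality does not count. One that does count, with onset on Days 8-14, lasts to about Days 22-28 and is still present at a Day 21 visit. Deaths, life-threatening events and serious surgical complications are unlikely to come to light only through a blood test.

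Most of this stands. What remains is asymptomatic autoimmune toxicity of Grade 2 or higher; persistent events that begin after Day 7 and resolve before a Day 35 visit under Schedule B; and Grade 3 laboratory events, if the reversibility clause applies to Grade 4 alone. Continuous recording does not help with an abnormality that nobody measures.

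On the immune samples, Table 1 specifies change from baseline and Section 15.7 names no Week 1 versus Week 2 contrast. That part is minor.

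**Conclusion.** The point holds in a limited form and should be fixed. The protocol permits 13 days of the endpoint period (Days 2-14) without a scheduled CBC or CMP or, after discharge by Day 7, 7 of the 14 days (Days 8-14) without any scheduled examination or laboratory test. Toxicities detectable only by laboratory test or examination may be missed or not be datable to before or after Day 14. This makes the primary percentage and the Table 4 count less reliable. How often sites would use the edges of the windows, and how many events would be affected, cannot be derived from the documents, so neither the size nor the direction of the error is claimed. The suspension figures under assumed missed shares show sensitivity only. The sample size and Table 5 need no change.

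**What to change.** 1. **Table 2, footnote a, and Section 12.4.** Narrow the early windows, for example Week 1 = Day 7 ± 2 (Days 5-9), Week 2 = Day 14 with 0 to +3 (Days 14-17), and Week 4 = Day 28 ± 3 (Days 25-31). Keep ±7 days from Week 8. Weeks 1 and 2 are then 14 − 9 = 5 to 17 − 5 = 12 days apart, and the Week 2 examination and CBC/CMP close out the period. A symmetric window would not do this: even Day 14 ± 3 allows a visit on Day 11.
2. **Sections 15.4.1 and 15.4.2.** Assign events to the 14-day endpoint by onset date. Count an abnormality first found at the Week 2 visit as within the period unless onset after Day 14 is documented. Without this default, a Day 15-17 result would recreate the dating problem.
3. **Section 15.7.** Analyse immune and titer data by actual day since infusion.

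**Cost.** Amendment wording, a few more minor visit-window deviations and a slightly conservative toxicity count. No visits, blood or patients are added.

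**Limit.** There would still be no scheduled CBC or CMP on Days 2-13, because Week 1 has none. An abnormality that arises and resolves within those days would remain unseen. Adding one at Week 1 would take about 6 mL (Table 3) and is a separate decision.

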12.1 Screening Examination

The screening examination will take place within 2 weeks before catheter placement. An informed consent must be signed by the patient and their legal guardian(s) before any study-specific screening procedure takes place. Within 6 months before receiving the PVSRIPO infusion, the patient should have received a PV booster, a serum test for LSQ and anti-tetanus toxoid IgG. The patient should also have whole blood drawn (up to 10 mL; red top tube(s)) for immunologic analysis and PV titer and an additional amount (up to 36 mL; yellow top ACD tube(s)) for other immunologic analysis during this time. Blood volumes drawn for immunologic analyses should not exceed 3 mL/kg in a 24 hour period or 7 mL/kg in an 8 week period, allowable per Duke policy. At the discretion of the investigator, blood volumes for immunologic analysis should be adjusted depending upon the weight of the child, in order to be consistent with Duke policy.

Pre-treatment evaluations within 2 weeks before catheter placement to determine eligibility and as a baseline will include the following, unless otherwise indicated:

- History and physical exam, including a full neurologic assessment and KPS or Lansky, within 2 weeks of catheter placement and within 5 days of PVSRIPO infusion
- Laboratory Evaluations:
 - CBC with differential
 - CMP
 - PT, aPTT
 - Beta-HCG, if appropriate (within 48 hours of catheter placement and PVSRIPO)
 - Anti-tetanus toxoid IgG (within 6 months of catheter placement and PVSRIPO)
 - LSQ (within 6 months of catheter placement and PVSRIPO)
 - Whole blood (up to 10 mL) for immunologic analysis and poliovirus titer
 - Whole blood (up to 36 mL, but not to exceed 3 mL/kg in a 24 hour period or 7 mL/kg in an 8-week period) for immunologic analysis (volumes drawn will be adjusted at the discretion of the Investigator, but will be based on the weight of the child to be consistent with Duke policy)
- Baseline MRI of the brain within 5 days of starting treatment

If a subject does not receive PVSRIPO, minimal records regarding the subject and the reason for screen failure will be retained in the study database.

12.2 Run-In Period

Not applicable.

12.3 Treatment Period

Day 0

- Biopsy and catheter placement
- After obtaining tissue for the standard clinical pathologic testing, up to three additional core biopsies will be obtained for molecular genetic tests (Section 9.1.4)
- CT of the brain to confirm catheter placement \geq 1 cm from the ventricles prior to beginning infusion
- PVSRIPO infusion (infusion may be same day or within a +1 day window)

12.4 Follow-up Period

Day 1 post infusion

- History and physical exam, including a full neurologic assessment, to be performed **daily** until discharged from the hospital
- CBC with differential
- CMP
- Whole blood (up to 4 mL) for immunologic analysis

Week 1 (+/- 1 week)

- History and physical exam, including a full neurologic assessment and KPS
- Whole blood (up to 10 mL) for immunologic analysis and PV titer
- Whole blood (up to 36 mL, but not to exceed 3 mL/kg in a 24 hour period or 7 mL/kg in an 8-week period) for immunologic analysis at the discretion of the Investigator

Week 2 (+/- 1 week)

- History and physical exam, including a full neurologic assessment and KPS
- CBC with differential
- CMP
- Whole blood (up to 6 mL) for immunologic analysis and PV titer
- Whole blood (up to 36 mL, but not to exceed 3 mL/kg in a 24 hour period or 7 mL/kg in an 8-week period) for immunologic analysis at the discretion of the Investigator

Week 4 (+/- 1 week)

- History and physical exam, including a full neurologic assessment and KPS
- MRI of the brain with gadolinium contrast
- CBC with differential
- CMP
- Whole blood (up to 10 mL) for immunologic analysis and PV titer
- Optional whole blood (up to 36 mL, but not to exceed 3 mL/kg in a 24 hour period or 7 mL/kg in an 8 week period) for immunologic analysis at the discretion of the Investigator

Week 8 (+/- 1 week)

- History and physical exam, including a full neurologic assessment and KPS
- MRI of the brain with gadolinium contrast
- CBC with differential
- CMP
- Whole blood (up to 10 mL) for immunologic analysis and PV titer
- Whole blood (up to 76.5 mL, but not to exceed 3 mL/kg in a 24 hour period or 7 mL/kg in an 8 week period) for immunologic analysis at the discretion of the Investigator

Weeks 16, 24, 32, 40, 48 (+/- 1 week)

- History and physical exam, including a full neurologic assessment and KPS
- MRI of the brain with gadolinium contrast
- CBC with differential
- CMP
- Whole blood (up to 10 mL) for immunologic analysis and PV titer (weeks 16 and 24 only)
- Whole blood (up to 76.5 mL, but not to exceed 3 mL/kg in a 24 hour period or 7 mL/kg in an 8 week period) for immunologic analysis (weeks 16 and 24 only) at the discretion of the Investigator

After week 48, patient will follow-up at the discretion of the treating physician.

- Whole blood (up to 10 mL) for immunologic analysis and PV titer (At the discretion of the Investigator, this blood sample, at least 2 years post-study drug infusion, may be obtained.)
- Whole blood (up to 76.5 mL, but not to exceed 3 mL/kg in a 24 hour period or 7 mL/kg in an 8 week period) for immunologic analysis (At the discretion of the Investigator, this blood sample, at least 2 years post-study drug infusion, may be obtained.)

Patients may not be treated with any other modality (other than bevacizumab per the ‘special considerations’ in Section 9.1.6) unless progressive tumor is noted or they are otherwise removed from the study. Patients will be considered off study upon tumor progression or upon treatment of the tumor with another modality. When subjects are considered off study, this indicates that subjects will no longer be obligated to undergo study-related tests and procedures, but the data described below will still be collected from these subjects as feasible. Subjects will be followed for serious adverse events for 30 days after coming off study. Collection of the following additional data from off study subjects will be performed, if possible, but is not mandatory and will not be considered a deviation if the data cannot be obtained. Subjects’ medical records will be reviewed for the remainder of their life, in order to collect data on subsequent treatments, disease progression, tumor size/volume, and survival. Follow-up activity will be at the discretion of the treating physician.

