Special Consideration: In the event that a patient demonstrates neurologic or radiographic signs suggestive of an inflammatory reaction secondary to the immune response triggered by PVSRIPO that requires a dose of dexamethasone above 4 mg a day after the first 2 weeks post PVSRIPO infusion, dexamethasone will not be increased any further. Instead, patients will be treated with bevacizumab 7.5 mg/kg IV every 3 weeks and neuroimaging (MRI) after 3 doses (every 9 weeks +/- 2 weeks) to assess if further treatment with bevacizumab is needed to control the cerebral inflammation. Bevacizumab will not be provided by the study. Every attempt should be made to discontinue dexamethasone. Once patients start bevacizumab, the follow-up visit schedule will be adjusted to coincide with the timing of the bevacizumab instead of the prior PVSRIPO infusion. Therefore, patients will return approximately every 9 weeks for an evaluation with MRI.

Per the packet insert for bevacizumab dated 12/2017, the safety and effectiveness of bevacizumab have not been established in the pediatric population ³³. Bevacizumab is currently not approved by the FDA for use in patients under the age of 18 years. “In published literature reports, cases of non-mandibular osteonecrosis have been observed in patients under the age of 18 years who have received Avastin ³³.” In initial Phase I and II clinical trials, four potential bevacizumab-associated safety signals were identified: hypertension, proteinuria, thromboembolic events, and hemorrhage. Additional completed Phase II and Phase III studies of bevacizumab in adults, as well as spontaneous reports have further defined the safety profile of this agent. Bevacizumab-associated adverse events identified in Phase III trials in adults include congestive heart failure (CHF) primarily in metastatic breast cancer, gastrointestinal perforations, wound-healing complications, and arterial thromboembolic events (ATEs). These and other safety signals are described in further detail in the bevacizumab package insert.

If there are adverse events or other circumstances prohibiting the use of bevacizumab, we will use corticosteroids or surgery, or other interventions deemed more appropriate for the patient by the treating physician, if needed, to treat the inflammatory reaction secondary to PVSRIPO.

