15.4.1 Overview of Study Design and Monitoring

Patients will be treated with PVSRIPO, then carefully monitored for safety for at least 1 year after treatment. Of particular interest will be the incidence of AEs that occur during the first 14 days after PVSRIPO treatment and the inflammatory events that occur during the first year after PVSRIPO treatment. The experience with PVSRIPO treatment of adult patients with recurrent WHO grade IV malignant glioma suggests that a patient remains at risk, during the first 12 months post-PVSRIPO treatment, of demonstrating neurologic or radiographic signs suggestive of an inflammatory reaction secondary to the immune response triggered by PVSRIPO that requires a dose of dexamethasone above 4 mg a day. As described in Section 9.1.6, such patients will be treated with bevacizumab 7.5 mg/kg IV every 3 weeks if possible, or alternatively corticosteroids or surgery.

Two sets of safety monitoring guidelines are proposed, with one focused on acute toxicity (i.e. occurring during the first 14 days after PVSRIPO administration), and one focused on long-term issues.

Acute Toxicity Monitoring Guidelines: Monitoring rules based upon the occurrence of an unacceptable toxicity, as defined in Section 9.1.5, during the first 14 days after PVSRIPO administration are shown below in **Table 4**.

If the number of patients with an unacceptable toxicity surpasses the noted thresholds, accrual will be suspended. Data will be carefully reviewed to determine if accrual should be terminated, continued without modification, or continued with appropriate modification (e.g. PVSRIPO dose reduction).

Table 4. Acute Toxicity Monitoring Rules.

# of Patients Accrued	Accrual Suspension Threshold
0 – 6	≥2 patients with unacceptable toxicity
7-9	≥3 patients with unacceptable toxicity
10-12	≥4 patients with unacceptable toxicity

The probability of study suspension and the expected number of treated patients before study suspension is tabulated below in **Table 5** as a function of the true underlying probability of an unacceptable toxicity.

Table 5. Probability of study suspension.

True Underlying Probability of a Unacceptable Toxicity within 14 days of PVSRIPO administration	Probability of Accrual Suspension	Expected Number of Patients to be Accrued
0.05	0.030	11.8
0.10	0.124	11.1
0.15	0.262	10.2
0.20	0.411	9.2
0.25	0.560	8.1
0.30	0.681	7.2
0.35	0.792	6.2
0.40	0.873	5.4

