Long-term Monitoring: If any patient experiences an inflammatory reaction that does not improve within 18 weeks of commencing bevacizumab or steroid treatment, the inflammatory reaction will be considered “irreversible.” If a patient experiences “irreversible” inflammatory reaction, further enrollment of patients on the PVSRIPO trial will be temporarily interrupted and data on all previously treated patients will be carefully reviewed to determine if the study needs modification. Options may include dose reductions in future patients (next PVSRIPO dose would be 3.3×10^6 TCID50), modification of the approach to treating a patient with an inflammatory reaction, study termination, or accrual continuation without modification.

The FDA and/or the DSMB for this study may be part of this decision-making in the event that there are unacceptable toxicities or inflammatory issues.

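### Required follow-up ends at Week 48, about four weeks short of the 12-month inflammatory risk period, and steroid-managed reactions have no assessment tied to the 18-week rule

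*Combined protocol and SAP*

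**What the plan says.** Section 15.4.1 says that patients will be treated, "then carefully monitored for safety for at least 1 year after treatment"; Section 5.5 says the same. The reason given is that adult experience "suggests that a patient remains at risk, during the first 12 months post-PVSRIPO treatment" of an inflammatory reaction needing treatment. The long-term rule in 15.4.1 calls a reaction irreversible, and interrupts enrolment for a data review, if it "does not improve within 18 weeks of commencing bevacizumab or steroid treatment".

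The schedule is in Section 12. In Table 2 the late visits fall on days "112, 168, 224, 280, 336" (Weeks 16 to 48), and a footnote adds: "Starting with Day 7 (Week 1), all tests and procedures have a 7-day plus or minus window". Section 12.4 then states: "After week 48, patient will follow-up at the discretion of the treating physician". Section 13.1 sets the recording period for adverse events (AEs) as running from the first study-related procedure "until their last study-related procedure, all AEs must be recorded". It names no week, and Table 2 marks AE collection after infusion as continuous.

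For patients who start bevacizumab, Section 9.1.6 moves the visit schedule to the bevacizumab start, with "neuroimaging (MRI) after 3 doses (every 9 weeks +/- 2 weeks". No end date is given for that cycle. Where bevacizumab cannot be used, the same section allows corticosteroids, surgery or other measures, and does not re-time the visits.

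**The concern.** The monitoring period and the visit schedule do not match. The plan defines a 12-month period of risk and promises to cover it, but the last required contact comes before it ends. This affects patients who are still on study, without progression, at Week 48.

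Two things are at stake. The first is the primary objective. Section 15.4.2 reports the proportion of patients needing bevacizumab or steroids for an inflammatory reaction, with a Kaplan-Meier summary of time to initiation. A start in the last weeks of the risk year enters those results only if a discretionary visit happens to record it.

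The second is the long-term rule. Section 7.3 describes peri-tumoral inflammation as the main toxicity attributable to the agent. The numerical thresholds in Table 4 cover only the first 14 days, so the 18-week rule is the one explicit trigger for later inflammation. It can work on time only if someone is required to assess the patient at or soon after 18 weeks from the start of treatment. On the steroid route, nothing requires that.

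**Working it through.** **Inputs.** Last fixed visit Week 48 and window ±7 days (Table 2, Section 12.4). Risk period 12 months, taken as 365 days (15.4.1). Rule clock 18 weeks from start of bevacizumab or steroids (15.4.1). Bevacizumab visits about every 9 weeks, MRI window ±2 weeks (9.1.6).

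**1. The plan's own days.** 16, 24, 32, 40 and 48 weeks × 7 = 112, 168, 224, 280 and 336. Table 2 is reproduced.

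**2. Gap to the end of the risk year.**
- Nominal: 365 − 336 = 29 days.
- Visit a week late (day 343): 365 − 343 = 22 days.
- Visit a week early (day 329): 365 − 329 = 36 days.

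**3. AE recording.** Section 13.1 ties the end of recording to the last study-related procedure. The last required one is the Week 48 visit; the only later item is an optional blood sample at 2 years or more. That recording in effect ends at Week 48 is therefore an inference, not a statement in the plan. The 30-day follow-up for serious adverse events in 12.4 would reach 336 + 30 = day 366 if it started at Week 48. The text starts it on coming off study (progression or another tumor treatment), and it covers serious events only.

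**4. The 18-week rule on the steroid route.** Visits stay at Weeks 8, 16, 24, 32, 40 and 48 after infusion.
- A visit falls exactly 18 weeks after the start only for starts at 24 − 18 = 6, 32 − 18 = 14, 40 − 18 = 22 or 48 − 18 = 30 weeks.
- A start just after one of the first three of these waits almost a full 8-week interval. Stepping by day over starts from Week 2 to Week 30, the longest delay is 7.9 weeks. Giving each start day equal weight, the mean delay is about 3.6 weeks, and 27% of start days have a nominal visit within a week of the 18-week date.
- The latest start whose 18-week date falls within required visits is 48 − 18 = Week 30, or 49 − 18 = Week 31 with the window. Starts at Weeks 31, 40 and 52 reach 18 weeks at Weeks 49, 58 and 70.

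**5. The 18-week rule on the bevacizumab route.** 2 × 9 = 18, so the second re-timed visit is nominally at 18 weeks whatever the start week. For starts after about Week 30 that visit lies beyond Week 48. Section 9.1.6 gives the cycle no end, and the Week 48 sentence in 12.4 makes no exception for it. The documents do not settle which governs.

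**The case against.** The strongest reply is that bevacizumab is the main route, and there the plan does provide an 18-week visit. That stands. A reader might infer that no visit falls at the 18-week point for anyone, or that 22 of 52 onset weeks (31 to 52, or 42%) cannot be classified and hence that 42% of reactions escape the rule. The documents do not support this. The week count is firm only for steroid-managed patients. For bevacizumab patients it depends on reading Week 48 as the end of the re-timed visits. Turning weeks into a share of reactions would need uniform onset, for which the documents give no basis.

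A reader might also note that the ±2-week MRI window permits a scan at 16 weeks, with the next at 25 to 29 weeks (27 ± 2), a delay of 7 to 11 weeks past week 18. That is a worst case. It applies only to a patient who has not improved at an early scan, and the rule does not require the judgment to rest on MRI.

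Other replies carry weight:
- The 18-week rule is not the only protection for accrual. The DSMB-Plus can recommend stopping (13.7), the investigator and statistician review accumulating AEs (13.1.2), and serious events reach the sponsor within 24 hours (13.2.1).
- The second primary proportion has no 12-month cut-off, so late reactions are not excluded by definition. Section 9.1.8.1 also asks for corticosteroid use to be recorded, without an end date. What is missing is a required contact at which late starts would be found.
- A reader might infer that withdrawn patients are followed longer than completers, because 12.6.2 specifies a year. That section does not say when the year begins and accepts a contact in place of a visit, so the comparison cannot be made.
- Removal of the 14-day accrual hold adds little here. A two-week hold would not have kept enrolment waiting for an 18-week classification. With five patients treated when it was lifted (5.5) and a maximum of 12, at most 12 − 5 = 7 remained.

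**Conclusion.** The concern holds in two parts. First, required visits stop 29 days (22 to 36) before the end of the risk period the plan itself defines and promises to monitor. Late reactions and treatment starts in that interval have no required capture for the second primary proportion or the time-to-initiation analysis; they may be missed, rather than certainly being lost. This rests on taking 12 months as 365 days and on the inference that AE recording in effect ends with the Week 48 visit.

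Second, the 18-week rule has no assessment attached to it on the steroid route. The next fixed visit can be up to about 8 weeks late, and none is required for starts after about Week 30 (31 with the window). On the bevacizumab route a nominal 18-week visit exists, and the defect is only that its continuation past Week 48 is unstated. How many patients this touches cannot be derived, since the plan gives neither an onset distribution nor an expected split between the two routes. The plan should be amended, because the promise is explicit and the remedy is cheap.

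**What to change.** (a) In 12.4 and 13.1, extend required recording of AEs and of bevacizumab and steroid use to day 365, with one telephone contact at day 365 for each patient still on study.

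(b) Reconcile 12.4, 9.1.6, 13.1 and 15.4.1 so that the existing 18-week rule, unchanged, has a stated assessment on both the bevacizumab and the steroid routes. State whether that assessment remains required after Week 48 until the reaction is classified, and whether the 9-week bevacizumab visits continue beyond that point. Visit and MRI timing are for the sponsor to set.

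The cost is amendment wording, one contact per patient still on study, and an occasional late visit for a late reaction. If that visit includes MRI, a young child may need sedation, which 9.1.6 lists as a risk. With at most 12 patients treated, the added burden is small.
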